## 1.9.9 Biomarkers

Not applicable.

# 1.9.10 Health-related Quality of Life (HRQoL)

## EQ-5D

The EQ-5D is a questionnaire with 5 questions (regarding mobility, self-care, usual activities, pain/discomfort, and anxiety/depression) each with three categories (no problem, moderate problem, severe problems) and a health state assessment from 0 (worst possible health state) to 100 (best possible health state). The number and percentage of subjects in each of the three categories for each question will be presented by visit and treatment group. Chi-square tests will be used to compare treatments groups by visit.

Summary statistics will be shown for the health state assessment by visit and treatment group.

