#### Secondary objectives

- To assess the efficacy of secukinumab 150 mg or 300 mg with respect to PASI 50/75/90/100 response and IGA 0 or 1 response, compared to placebo over time in subjects who were PASI 75 responders at Week 52, over time for subjects who were re-treated after relapse with secukinumab 150 mg or 300 mg, and over time in subjects who were partial responders at Week 52.
- To assess the efficacy of secukinumab 150 mg or 300 mg with respect to PASI score and IGA mod 2011 score, compared to placebo over time in subjects who were PASI 75 responders at Week 52, over time for subjects who were re-treated after relapse with secukinumab 150 mg or 300 mg, and over time in subjects who were partial responders at Week 52.
- To assess time to PASI 75 response **for subjects who were re-treated after relapse with secukinumab 150 mg or 300 mg.**
- To assess the efficacy of secukinumab 150 mg or 300 mg in subjects with moderate to severe chronic plaque-type psoriasis with respect to loss of IGA 0 or 1 response, compared to placebo **in subjects who were PASI 75 responders and IGA 0 or 1 responders at Week 52.**
- To assess time to IGA 0 or 1 response for subjects who were IGA 0 or 1 responders at re-randomization, and who lost IGA 0 or 1 response during randomized withdrawal, and **who were re-treated after relapse with secukinumab 150 mg or 300 mg.**
- To assess the clinical safety of secukinumab 150 mg or 300 mg as assessed by vital signs, clinical laboratory values, electrocardiograms (ECGs), and adverse events (AEs) monitoring,

compared to placebo in subjects who were PASI 75 responders at Week 52, in subjects who were re-treated after relapse with secukinumab 150 mg or 300 mg, and in subjects who were partial responders at Week 52.

- To assess the efficacy of secukinumab 150 mg or 300 mg in subjects with moderate to severe chronic plaque-type psoriasis with respect to changes in Dermatology Life Quality Index® (DLQI®), compared to placebo over time in subjects who were PASI 75 responders at Week 52, over time for subjects who were re-treated after relapse with secukinumab 150 mg or 300 mg, and over time in subjects who were partial responders at Week 52.

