- To assess the efficacy of secukinumab 150 mg or 300 mg in subjects with moderate to severe chronic plaque-type psoriasis with respect to DLQI 0 or 1 achievement, compared to placebo over time in subjects who were PASI 75 responders at Week 52, over time for subjects who were re-treated after relapse with secukinumab 150 mg or 300 mg, and over time in subjects who were partial responders at Week 52.
- To assess the efficacy of secukinumab 150 mg or 300 mg in subjects with moderate to severe chronic plaque-type psoriasis with respect to EuroQOL 5-Dimension® Health Questionnaire (EQ-5D®) score, compared to placebo over time in subjects who were PASI 75 responders at Week 52, over time for subjects who were re-treated after relapse with secukinumab 150 mg or 300 mg, and over time in subjects who were partial responders at Week 52.
- To investigate the effects of treatment with secukinumab 150 mg or 300 mg on the occurrence of rebound following cessation of therapy, in subjects who were PASI 75 responders at Week 52, for subjects who were re-treated after relapse with secukinumab 150 mg or 300 mg, and in subjects who were partial responders at Week 52.
- To assess the efficacy of secukinumab 150 mg or 300 mg in subjects with moderate to severe chronic plaque-type psoriasis with respect to relapse, compared to placebo **in subjects who were PASI 75 responders at Week 52.**
- To investigate the development of immunogenicity (IG) against secukinumab over time.

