## **6.6 Other assessments**

These includes (as indicated in [Table 6-1](#))

- Waist circumference and hip circumference
- Fasting laboratory evaluations,
- HRQoL assessments such as

1. DLQI®
  2. EQ-5D®
  3. HAQ®-DI (subjects with PsA at baseline of the core study)
- PK assessments will be done as indicated in [Table 6-1](#).

Note: EQ-5D assessments will not be performed during the open label period.

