## 9 Data analysis

Treatment groups for analysis will include:

- **Subjects who were PASI 75 responders at Week 52**
  - Secukinumab 150 mg
  - Secukinumab 300 mg
  - Placebo (secukinumab 150 mg in core studies)
  - Placebo (secukinumab 300 mg in core studies)
- **Subjects who were re-treated after relapse with secukinumab 150 mg or 300 mg**
  - Secukinumab 150 mg
  - Secukinumab 300 mg

- Subjects who were partial responders at Week 52
  - Secukinumab 150 mg
  - Secukinumab 300 mg

For open-label period analyses subjects being switched from 150 mg to 300 mg will be summarized as well.

NOTE: Week 52 assessments refer to Baseline extension assessments

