### 9.5.3 Health-related Quality of Life (HRQoL)

#### EQ-5D®

The EQ-5D® is a questionnaire with 5 questions (regarding mobility, self-care, usual activities, pain/discomfort, and anxiety/depression) each with three categories (no problem, moderate problem, severe problems) and a health state assessment from 0 (worst possible health state) to 100 (best possible health state). The number and percentage of subjects in each of the three categories for each question will be presented by visit and treatment group. Summary statistics will be shown for the health state assessment by visit and treatment group.

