## 1.1 Statistical and analytical plans

The planned analysis is described in Section 9 (Data Analysis) of the study protocol which is available in Appendix 16.1.1 of the CSR.

This document mainly covers statistical and analytical plans for the final analysis after database lock. The key analyses which conducted previously might be re-run using the final data.

The key secondary analyses during RW period using the final data will be re-run for PASI 75 responders at week 52. The re-run analyses are including summary and analysis of PASI 50/75/90/100 response and IGA 0 or 1 response, loss of PASI 75/IGA 0 or 1 response, time to relapse, and DLQI. Since loss of PASI 75 during randomized withdrawal period will be re-run, the primary endpoint – loss of PASI 75 up to week 68 will not be performed in the final analysis. In addition, a summary of PASI 50/75/90/100 response and IGA 0 or 1 response and IGA 0 or 1 response till week 156 will also be provided using retreatment patients after relapse.

Summary statistics for continuous variables will include N, mean, standard deviation, minimum, lower quartile, median, upper quartile, maximum. Summary statistics for discrete variables will be presented in contingency tables and will include absolute and relative frequencies.

If not otherwise specified, p-values will be presented as two-sided p-values and two-sided confidence intervals will be displayed.

Unless otherwise stated, the level of significance will be set to 5% (two-sided, family-wise type-I-error).

All listings will be presented by treatment sequence.

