For final analysis, the following treatment groups will be reported for the on treatment period.

AIN457 150 mg stay AIN457 300 mg stay All AIN457 150 mg All AIN457 300 mg AIN457 150 mg only AIN457 150 mg - 300 mg AIN457 300 mg only

The following study periods will be considered for analysis:

- Screening period (before Randomization in extension)
- **Randomized** withdrawal (RW) period for subjects who were PASI 75 responders at Week 52- the duration of RW period for each subject is different i.e., starting from Week 52 until the subject experiences the first full relapse for efficacy analyses and until the subjects reinitiating the secukinumab after first full relapse for safety analyses. RW period is not fixed for all the subjects but varies for subject to subject based on occurrence of relapse. Subjects not experiencing the relapse will end their RW period at Week 156.
- **Treatment** period for subjects with relapse (for efficacy analyses it is starting from the visit in RW period at which a subject experiences first full relapse to Week 156. Safety analysis will not be re-run for subjects with relapse).
- **Treatment** period for subjects with partial response (Week 52 to Week 156)
- **Open label** period for subjects who were continued in the study and were unblinded at Week 156. The first open label dose were given at the site at Week 156. Subjects previously randomized to receive 150 mg secukinumab may continue with 150 mg secukinumab open label or may switch to 300 mg s.c. at the discretion of the investigator. Subjects previously randomized to 300 mg secukinumab continued with 300 mg secukinumab open label. Placebo subjects who entered the open label period were given once weekly s.c. injections of secukinumab for 4 consecutive weeks and then s.c. injections every 4 weeks. Any subject starting on secukinumab 150 mg may continue on 150 mg every 4 weeks or switch to 300 mg at Week 156 or any other regular site visit if the investigator decided the subject would benefit from the higher dose. The Week 244 visit was the last scheduled visit at which the subjects were allowed to switch to 300 mg dose. Decreasing the dose from 300 mg to 150 mg was not allowed.
- Follow-up (FU) period (for all subjects)\*: treatment free period (Week 264 to Week 268).

Novartis	Confidential	Page 15
RAP Module 3	9-Apr-2018 (1:15)	Secukinumab / AIN457A2302E1

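### The final-analysis SAP plans no placebo column for EQ-5D, PASI score or IGA score, and adds EQ-5D chi-square tests among unnamed, partly nested groups

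*SAP*

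**What the plan says.** **Protocol.** Section 2.2 sets an EQ-5D objective on the "score, compared to placebo over time in subjects who were PASI 75 responders at Week 52". A parallel objective assesses efficacy "with respect to PASI score and IGA mod 2011 score, compared to placebo over time in subjects who were PASI 75 responders at Week 52". Section 9 lists the analysis groups for these subjects as the two secukinumab doses and the two matching placebo arms. For EQ-5D, section 9.5.3 plans description only: "The number and percentage of subjects in each of the three categories for each question will be presented by visit and treatment group". Section 9.5.1 likewise plans summaries of PASI score and IGA score by visit and treatment group. Section 6.6 adds: "Note: EQ-5D assessments will not be performed during the open label period".

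**SAP.** Section 1.1 lists what will be re-run for the randomised withdrawal (RW) period: the PASI and IGA response variables, "loss of PASI 75/IGA 0 or 1 response, time to relapse, and DLQI". EQ-5D, PASI score and IGA score are not on that list. Section 1.3 then states: "For final analysis, the following treatment groups will be reported for the on treatment period". It names seven groups, all secukinumab. Section 1.9.10 repeats the protocol's EQ-5D summary and adds one sentence: "Chi-square tests will be used to compare treatments groups by visit".

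**The concern.** The randomised withdrawal design gives each dose its own placebo arm between Week 52 and Week 156. That contrast is what the three objectives ask for. If the three variables appear only in secukinumab groups, the final report cannot set secukinumab beside placebo for them.

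EQ-5D is the sharpest case. With no EQ-5D assessments in the open label period, its data come from the years when the placebo arms existed. Tabulating it only in on-treatment groups leaves the placebo experience out.

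The chi-square sentence raises a second problem. A Pearson chi-square assumes that the groups share no subjects, and several of the seven groups do. Any p-value from on-treatment groups, nested or not, would also sit beside a placebo objective that it does not test.

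**Working it through.** **Where each variable is scheduled**

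| Place | EQ-5D, PASI score, IGA score | DLQI, for contrast |
|---|---|---|
| Protocol 2.2 | Against placebo, PASI 75 responders | Same |
| Protocol 9.5.1 and 9.5.3 | Summaries by visit and treatment group | Summaries, plus Van Elteren and Fisher tests against placebo |
| SAP 1.1, RW re-run list | Absent | Present |
| SAP Table 1-2, RW row | Absent | Present |
| SAP Table 1-4 | On-treatment period only | RW and on-treatment |
| SAP Table 1-9 | Final analysis only | Final analysis and RW re-run |

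The SAP is not consistent with itself. Section 1.9.5 still lists the three variables as secondary variables in Week 52 PASI 75 responders. Section 1.9.4 gives them LOCF rules under its heading for RW re-runs. No scheduled RW analysis uses either.

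**The seven groups (Table 1-2, footnotes 7 to 13)**

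- *150 mg stay* (PASI 75 responders never up-titrated) lies within *150 mg only* (which adds partial responders).
- *150 mg only* and *150 mg - 300 mg* both lie within *All 150 mg*.
- *300 mg stay* lies within *300 mg only*, which lies within *All 300 mg*.
- *All 150 mg* and *All 300 mg* do not overlap, because up-titrated subjects stay in the former.
- Randomised placebo subjects enter only the *All* groups, only if they relapsed and were re-treated, and only from 16 weeks after re-treatment, counted as secukinumab.

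**Planned size.** The sample-size section gives 414 subjects per dose at 2:1. That is 414 × 2/3 = 276 on secukinumab and 414 × 1/3 = 138 on placebo, matching the stated figures. Over two doses, 2 × 138 = 276 placebo subjects have no placebo column.

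**Chi-square between a subset and its parent.** Let the subset be a share f of the parent group, with n subjects in the subset.

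- True variance of the difference in proportions: proportional to (1/n)(1 − f).
- Variance assumed by the test: proportional to (1/n)(1 + f).
- Ratio r = (1 − f)/(1 + f), always below 1, so the test is conservative.

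For a two-category outcome the actual size is 2 × [1 − Φ(1.96/√r)]:

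- f = 0.5: r = 0.333, size 0.07%.
- f = 0.7: r = 0.176, size 0.0003%.

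For a three-category EQ-5D item (2 degrees of freedom) it is exp(−5.991/(2r)). At f = 0.5 this gives exp(−8.99) = 0.01%.

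**Simulation with no true difference, nominal 5%.** Inputs not in the documents, and therefore assumed: category probabilities 0.60/0.35/0.05; 276 responders per dose; partial responders 10–20% and re-treated placebo subjects 25% of that number; up-titration 20–60%.

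| Comparison | Rejection rate |
|---|---|
| *150 mg stay* against *All 150 mg* | 0.0–0.6% |
| One test over all seven groups | 3.6–4.7% |
| Disjoint: *All 150 mg* against *All 300 mg*; or *150 mg only*, *150 mg - 300 mg*, *300 mg only* | 4.6–5.6% |

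The 0.6% agrees with the formula. With 60% up-titration and 20% partial responders, f = 0.4/1.45 = 0.276, r = 0.568 and exp(−5.28) = 0.5%.

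A second set of assumptions (probabilities 0.70/0.25/0.05; 193 partial responders and 70 re-treated subjects per dose; 10–50% up-titrated) gave 0.00–0.03% for a nested pair, 3.6–4.0% over seven groups and 4–5% for disjoint dose groups.

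**Timing.** EQ-5D stops by Week 156 and up-titration starts at Week 156. *150 mg stay*, *150 mg only* and *150 mg - 300 mg* therefore sort EQ-5D data by a decision taken at or after the last EQ-5D assessment.

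**The case against.** The strongest reply is about scope. SAP section 1.1 says that the document mainly covers the final analysis and that key analyses done earlier might be re-run. Table 1-9 marks even the primary variable as not analysed here. Protocol section 9.6 plans an unblinded analysis of all data up to Week 68, when both placebo arms were running. A reader might infer that the randomised comparison was never made; the documents do not support that. What stands is narrower. This SAP neither plans the placebo presentation nor says where it was reported, and a Week 68 analysis would not cover the RW period to Week 156.

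Second, the protocol never planned a placebo test for these three variables. That stands: what is missing is the side-by-side summary, not a promised p-value. DLQI did have planned tests, which may explain why it is re-run.

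Third, a reader might call the chi-square tests invalid outright. The SAP names no pair of groups, and disjoint sets exist in which the test keeps nominal size. Invalidity is shown only for overlapping groups, and there the error is conservative, so no false-positive inflation follows. The sentence concerns EQ-5D only.

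Fourth, for PASI and IGA the SAP keeps RW comparisons with placebo on the response variables, by Cochran-Mantel-Haenszel test and logistic regression (section 1.9.6), and on loss of response. That reduces the loss for those two scales. No other EQ-5D analysis in the SAP does the same.

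**Conclusion.** The point holds for this final-analysis SAP. Three secondary variables with a stated placebo objective are scheduled only in groups without a placebo column, leaving 276 planned placebo subjects without a column of their own. Section 1.1.1 does not record this as a change from the protocol.

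The EQ-5D chi-square is a separate, smaller fault. It is absent from the protocol, from section 1.1.1 and from the overview of methods in section 1.9.1.3, and its groups are not named. Between nested groups it almost never rejects; between disjoint on-treatment groups it is near nominal but does not address placebo.

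The direction of the nested-group result follows from the variance ratio alone. The simulated percentages depend on assumed category probabilities and group shares. The count of 276 is a planning figure. None of these variables is in the alpha-controlled testing strategy, so the primary conclusion is unaffected.

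**What to change.** 1. In SAP Tables 1-4 and 1-9 (and the RW row of Table 1-2), add the RW period for EQ-5D, PASI score and IGA mod 2011 score. Summarise by visit for the four randomised groups, PASI 75 responders only. The restriction needs stating, because footnotes 1 and 2 of Table 1-2 also put partial responders into the two secukinumab groups. Alternatively, cite the earlier report that contains these summaries.
2. Delete the EQ-5D chi-square tests across the on-treatment groups, or restrict them to named, mutually exclusive groups.
3. If a test is kept to address the objective, compare each dose with its own placebo in the RW period, label the p-value nominal, and record the test in section 1.1.1.

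The cost is SAP wording and a few extra tables. The data are already collected, the DLQI RW analysis is a template, and section 1.9.4 already gives LOCF rules for these variables.

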- To assess the efficacy of secukinumab 150 mg or 300 mg in subjects with moderate to severe chronic plaque-type psoriasis with respect to DLQI 0 or 1 achievement, compared to placebo over time in subjects who were PASI 75 responders at Week 52, over time for subjects who were re-treated after relapse with secukinumab 150 mg or 300 mg, and over time in subjects who were partial responders at Week 52.
- To assess the efficacy of secukinumab 150 mg or 300 mg in subjects with moderate to severe chronic plaque-type psoriasis with respect to EuroQOL 5-Dimension® Health Questionnaire (EQ-5D®) score, compared to placebo over time in subjects who were PASI 75 responders at Week 52, over time for subjects who were re-treated after relapse with secukinumab 150 mg or 300 mg, and over time in subjects who were partial responders at Week 52.
- To investigate the effects of treatment with secukinumab 150 mg or 300 mg on the occurrence of rebound following cessation of therapy, in subjects who were PASI 75 responders at Week 52, for subjects who were re-treated after relapse with secukinumab 150 mg or 300 mg, and in subjects who were partial responders at Week 52.
- To assess the efficacy of secukinumab 150 mg or 300 mg in subjects with moderate to severe chronic plaque-type psoriasis with respect to relapse, compared to placebo **in subjects who were PASI 75 responders at Week 52.**
- To investigate the development of immunogenicity (IG) against secukinumab over time.

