#### DLQI®

The DLQI® measures functional disability of subjects with dermatological disorders that are greater than 18 years of age and had been utilized as a relevant clinical measure in atopic dermatitis, as well as other dermatitis clinical trials. The DLQI® is a simple, validated, self-administered 10-item questionnaire. The instrument contains six functional scales (i.e., symptoms and feeling, daily activities, leisure, work and school, personal relationships, treatment). For the DLQI®, each question will be answered with the following response: “not at all,” “a little,” “a lot,” or “very much”. Seven scores will be derived from the DLQI®: the total score of each of the six dimensions as well as the total score over all items. The higher the score, the more quality of life is impaired.

For each of the seven scores the percentage change from baseline will be derived. Summary statistics will be provided for absolute values as well as for the percentage change by visit and treatment group.

For the “subjects who were PASI 75 responders at Week 52” the following analysis will be performed as well:

The absolute value and the percentage change from baseline of DLQI® total score will be analyzed with the Van-Elteren test using type-II weights, for all pairwise comparisons between secukinumab treatment groups versus placebo. The Van-Elteren test will be performed at each visit. Language of the questionnaire and body weight stratum will be the strata adjusted for in the Van-Elteren test. In addition, stratified Hodges-Lehmann estimates for the median as well as confidence intervals will be derived for the absolute values and percentage change to baseline for each treatment group as well as for all pairwise comparisons between secukinumab treatment groups versus placebo.

It is understood that conclusions obtained from the confidence intervals of these estimates (mean or Hodges-Lehmann estimates for the median) will not be completely consistent with the testing results (Van-Elteren test) which constitute the key analysis for drawing conclusions.

In addition, summary statistics will be provided for number of subjects achieving DLQI 0 or 1. For the “subjects who were PASI 75 responders at Week 52” the secukinumab treatment groups will be compared to placebo by means of Fisher’s exact test.

[figure not shown]

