## 9.7 Sample size calculation

**Assumptions for the number of subjects eligible for randomized withdrawal (i.e for the analysis of primary endpoint):**

- Drop-out rate on secukinumab at Week 12 in core studies: 5% (estimate from CAIN457A2211)
- Drop-out rate on placebo at Week 12 in core studies: 15% (from CAIN457A2211)
- Placebo PASI 75 response rate at Week 12: 5% (conservative assumption)
- Drop-out rate on secukinumab up to Week 52 in core studies: 15% (common for secukinumab induction and placebo induction regimens, as in [Leonardi et al, 2008](#))
- PASI 75 response rate at Week 52 on secukinumab 150 mg in core studies: 65% (from dosing rationale in protocols of core studies) (power would be larger for 300 mg if we would assume similar loss of PASI75 rates)
- Type-I-error rate is defined to one-sided 2.5%

With these assumptions it is estimated to have 414 subjects eligible per dose to enter the randomized withdrawal, with a randomization ratio of 2:1 this would be 276 subjects on 150 mg and 138 subjects on placebo. With about 400 subjects the study would have more than 90% power to detect differences in the cumulative rates if 10% of subjects on secukinumab lost PASI 75 response versus 23% on placebo, PASS 2008 software (Log Rank Survival Power Analysis - Simple).

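### EQ-5D levels are ordered, but SAP 1.9.10 compares them with chi-square tests that name no ordinal version and no groups; under a common shift this costs about 6 to 10 points of power

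*SAP*

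**What the plan says.** SAP 1.9.10 describes the EQ-5D questions as "each with three categories (no problem, moderate problem, severe problems"). It plans counts and percentages by visit and treatment group, and adds: "Chi-square tests will be used to compare treatments groups by visit". It does not say which chi-square statistic is meant, which groups are compared, or whether the test is stratified. The default level is in SAP 1.1: "Unless otherwise stated, the level of significance will be set to 5% (two-sided, family-wise type-I-error").

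The test first appears in the SAP. Protocol 9.5.3 plans only description of the EQ-5D questions: "The number and percentage of subjects in each of the three categories for each question will be presented by visit and treatment group". SAP 1.1.1 does not list the test among the changes to the protocol's methods, and the overview table in SAP 1.9.1.3 marks EQ-5D for summary statistics only.

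For the DLQI total score in Week 52 PASI 75 responders, Protocol 9.5.3 does plan a rank test, which "will be analyzed with the Van-Elteren test using type-II weights, for all pairwise comparisons between secukinumab treatment groups versus placebo". The DLQI text in SAP 1.9.10 no longer carries it.

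Protocol 2.2 has a secondary objective "with respect to EuroQOL 5-Dimension", stated as a comparison with placebo over time in Week 52 PASI 75 responders. SAP Table 1-4 places EQ-5D only in the on-treatment period. Table 1-9 lists it for the final analysis without the RW re-run that DLQI has.

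**The concern.** No, moderate and severe problems form an ordinal scale. An ordinary chi-square test gives the same p-value if the three labels are shuffled, and it spends two degrees of freedom on a two-group comparison. A test on ordered scores uses one degree of freedom and points in a direction. If treatment moves subjects along the scale, the chi-square test is the less sensitive choice, and its p-value alone does not say which group did better.

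The sentence also leaves the compared groups open. The seven on-treatment groups in SAP 1.3 include no placebo group, and they overlap: the 150 mg stay group lies inside 150 mg only, which lies inside All 150 mg. The group switched from 150 mg to 300 mg is defined by open-label up-titration, whereas Protocol 6.6 stops EQ-5D collection before the open-label period. Neither a chi-square test nor a rank test is valid across overlapping samples.

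**Working it through.** **Inputs.** The documents state no EQ-5D effect size, level distribution or power. From the documents: three levels, two-sided 5%, and the planned sizes for one dose (Protocol 9.7), "with a randomization ratio of 2:1 this would be 276 subjects on 150 mg and 138 subjects on placebo". Assumed: the level distributions, a proportional-odds shift, and a two-group comparison of this size at one visit.

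**1. The plan's only power figure.** This is the primary log-rank comparison, stated as more than 90% with about 400 subjects.
- Hazard ratio = ln(0.90)/ln(0.77) = 0.403.
- Expected events = 400 × (2/3 × 0.10 + 1/3 × 0.23) = 57.3.
- Schoenfeld power at one-sided 2.5% = Φ(√(57.3 × 2/9) × |ln 0.403| − 1.96) = Φ(1.28) = 90.0%. With 414 subjects it is 91.0%.

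The figure reproduces, but it says nothing about EQ-5D.

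**2. Degrees of freedom.** A 2 × 3 table has (2 − 1) × (3 − 1) = 2 df; the rank test has 1 df. For a pure ordered shift both have about the same noncentrality λ. At 80% rank power, λ = (1.960 + 0.842)² = 7.85. A 2-df chi-square test with that λ has 70.9% power. The same step gives:

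| Rank test, 1 df | Chi-square, 2 df | Loss (points) |
|---|---|---|
| 50% | 40.1% | 9.9 |
| 60% | 49.5% | 10.5 |
| 70% | 59.7% | 10.3 |
| 80% | 70.9% | 9.1 |
| 90% | 83.5% | 6.5 |

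**3. Simulation under proportional odds.** 138 placebo and 276 secukinumab subjects, 40,000 tables per row, Pearson chi-square against the tie-corrected Wilcoxon test. The odds ratio (OR) multiplies both cumulative odds. For placebo 60/35/5% (no/moderate/severe) and OR 2.0, the odds of no problems go from 0.60/0.40 = 1.5 to 3.0, which is 75%. The odds of being below severe go from 19 to 38, which is 97.4%. Secukinumab is therefore 75.0/22.4/2.6%. Gains are taken before rounding.

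| Placebo levels | OR | Chi-square | Rank | Gain |
|---|---|---|---|---|
| 50/40/10% | 1.25 | 16.0% | 20.1% | 4.1 |
| 50/40/10% | 1.5 | 42.2% | 51.4% | 9.2 |
| 60/35/5% | 1.75 | 63.9% | 73.0% | 9.1 |
| 60/35/5% | 2.0 | 81.6% | 88.1% | 6.5 |
| 60/35/5% | 2.5 | 96.3% | 98.1% | 1.8 |
| 75/22/3% | 2.0 | 67.1% | 75.2% | 8.1 |
| 85/14/1% | 2.0 | 49.8% | 57.4% | 7.6 |
| 85/14/1% | 3.0 | 82.6% | 87.4% | 4.8 |
| 90/9.9/0.1% | 2.0 | 41.7% | 43.6% | 1.9 |

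With the near-empty distribution placed on secukinumab instead, 90/9.9/0.1% at OR 2.0 gives 60.7% against 64.2%, and 95/4.9/0.1% at OR 3.0 gives 82.0% against 84.9%. The severe column is then often empty and the table is nearly binary, so the two tests almost coincide.

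**4. Changes that are not a common shift.** If only the severe tail changes, 60/35/5% on placebo against 60/39/1%, chi-square has 64% power and the rank test 6.5%. For 60/30/10% against 70/20/10%, they have 53% and 44%.

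**5. Level and sparse cells.** With no effect, chi-square rejected in 4.9% (60/35/5%) and 4.6% (80/18/2%) of tables, and the rank test in 4.8% and 5.1%. At 60/35/5% and OR 2.0, 57% of tables had an expected count below 5. In these cases sparse cells do not inflate the Type I error.

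**The case against.** The strongest reply is that the plan does not commit to the losing method. A CMH mean-score statistic is also referred to a chi-square distribution and uses the order, and an analysis document that is not public may name it. This stands as a reason to name the statistic. It does not remove the point, because the SAP itself gives no such specification.

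The DLQI precedent is also weaker than it looks. It concerns a 0 to 30 total score, is stratified by questionnaire language and body weight rather than by the randomization strata, and is absent from the SAP's DLQI text. It shows only that a rank test was acceptable to this team. The lack of direction is partly met by the counts and percentages shown beside the test.

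A reader might infer several stronger things that the documents do not support:
- **A fixed power loss of 5 to 10 points.** Steps 3 and 4 show that it shrinks at low or very high power or with an almost empty severe level, and that it can reverse.
- **A loss that holds whichever groups are compared, or a much larger one from a single test across all seven on-treatment groups.** Those groups overlap, so a power figure based on independent columns has no basis.
- **A one-line change.** The placebo comparison is not in the SAP's EQ-5D analysis and has to be added.
- **An inflated error rate.** Step 5 shows none.

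**Conclusion.** The point holds in a limited form. SAP 1.9.10 applies chi-square tests to ordered levels without naming an ordinal statistic or the groups to be compared. For two independent groups of 276 and 138, two-sided 5%, a proportional-odds shift, rank-test power of about 50% to 90% and a severe level that is not almost empty, the loss is about 6 to 10 points. It is about 2 to 4 points when almost nobody is severe, and chi-square can be the better test when the change is not a common shift.

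None of these conditions is given in the documents, and the placebo-controlled layout behind 276 and 138 is not the one the SAP assigns to EQ-5D. Because subjects leave the RW period at relapse, later visits would have fewer subjects and a selected remainder. EQ-5D is a secondary endpoint outside the testing strategy (SAP 1.9.3), so the primary conclusion is unaffected. This is a desirable improvement, not a necessary one.

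**What to change.** 1. In SAP 1.9.10, replace the chi-square tests with a CMH row-mean-scores test using modified ridit scores on the three ordered levels of each dimension. Stratify by geographical region and the body-weight stratum used at randomization.
2. Name the pairs, and test only non-overlapping groups. To match the secondary objective, use secukinumab 150 mg against the placebo group that came from 150 mg, and 300 mg against the placebo group that came from 300 mg, in Week 52 PASI 75 responders during the RW period.
3. Add EQ-5D to the RW period in SAP Tables 1-4 and 1-9, and state the visits tested. The SAP's existing cut-off for the PASI comparisons, the last visit with more than 5% of placebo subjects remaining, could be reused.
4. Keep the frequency tables. They show a change confined to one level, which a rank test can miss. Leave the overlapping on-treatment groups descriptive.
5. List the test in SAP 1.1.1 as an addition to the protocol, and update the overview table in SAP 1.9.1.3.

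Cost: a few lines of SAP text, two table entries and a small extra analysis of data already collected. No descriptive output is lost, and the alpha-controlled tests do not change.
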